#### Radiographic Outcomes:

To assess radiographic stability as compared with other primary THR systems and similar dual mobility cups, radiographs will be taken and collected in the AP pelvis, AP femur and lateral views for the preoperative, 6-week, 1, 2, 3, 4 and 5-year intervals. Additional radiographs will be obtained at the 7-year and 10-year time points at investigational sites that choose to bring their subjects back in for these optional visits.

The AP pelvis and AP femur view allow for observation of any conditions involving the sacral wings, iliac bones, ischium, pubis as well as the femoral head and neck. The lateral view allows for evaluation of the entire hip joint as well as the femoral head, neck and proximal shaft. Suggested radiographic technique for the views required is included in Appendix A.

Radiographs will be evaluated by an independent reviewer throughout the course of the study. Radiographic analysis of the acetabular component will employ three zones (Zone 1 – Zone 3) in the AP view.  Radiographic analysis of the femoral component will employ seven zones (Zone 1 - Zone 7) in the AP views and seven zones (Zone 8 – Zone 14) in the lateral view. Numerous parameters will be reviewed by zone, including radiolucency, hypertrophy, condensation and migration. Radiolucency in at least 50% of a zone and measuring at least 1 mm in width is defined as radiolucency present. Cases that present with migration of greater than 5 mm in any direction or at least 2 mm radiolucency in all zones will be considered radiographic failures.

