#### Secondary:

- The Kaplan-Meier survival curve of revision/removal for the Restoration® ADM X3® Acetabular System (acetabular shell and insert) will be displayed.
- A paired t-test will evaluate the changes in clinical and patient outcomes (HHS, SF-12, EQ-5D, and LEAS), preoperative to 5 years postoperative within the Restoration® ADM X3® Acetabular System (acetabular shell and insert) group, when data is available. In addition, the mean scores (HHS, SF-12, EQ-5D, and LEAS) over time will be tabulated, with standard deviation and 95% confidence intervals presented, if applicable.
- The AE rates and radiographic data will be listed and tabulated at 10 years postoperative for the Restoration®
   ADM X3® Acetabular System group, with 95% confidence intervals presented, if applicable.

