### 7.4 Annual Follow-up Visits

Clinical data will be collected via office visit by the investigator at the following annual postoperative intervals: 1-year, 2-year, 3-year, 4-year and 5-year. Tools for postoperative evaluation will be the HHS, AP pelvis, AP femur and lateral radiographs. Radiographs will also be obtained at 1 year and then annually to 5 years postoperatively.

Patient outcomes data will also be collected with the required SF-12, LEAS, and EQ-5D patient questionnaires at each annual visit at the 1-year through 5-year follow-up visits.

All clinical data, radiographs, and patient outcomes data must be collected within  $\pm$  2 months of the 1-year and 2-year anniversary dates. For remaining annual time points, the window expands to  $\pm$  3 months of the 3-year anniversary date and  $\pm$  4 months of the 4-year through 10-year anniversary dates.

The initial phase of the study will continue for 5 years after surgery and include collection of the previously described radiographs, HHS, SF-12, LEAS and EQ-5D patient questionnaires. In the second phase of the study, all subjects will complete a brief Follow-up Questionnaire annually at the 6-year, 7-year, 8-year, 9-year and 10-year follow-up intervals. This form may be completed by the SC during a subject telephone interview, or by the subject either at home or during a clinic visit. The questionnaire will be used to obtain the following information, at a minimum:

- Subject satisfaction with the hip replacement
- Presence of any pain in the study hip
- Any surgeries performed on the study hip
- Any dislocations in the study hip

The questionnaire will also provide information on any revisions and enable calculation of the Kaplan-Meier Survival Curve necessary to meet the primary endpoint of the study.

Additionally, at investigational sites that choose to continue collecting clinical and radiographic data during the second phase of the study, subjects will be evaluated again at 7 and 10 years after surgery.

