### IMPORTANT PHYSICIAN INFORMATION

Bone Resorption and Osteolysis. Bone resorption can occur as a natural consequence of total joint arthroplasty due to changes in bone remodeling patterns. Bone remodeling is mediated by the changes in stress distribution caused by implantation. Extensive resorption around the prosthesis leads to implant loosening and failure. Localized progressive bone resorption due to reasons other than stress shielding or infection may occur around the prosthetic components as well as between the components and bone, and this has been termed osteolysis. It is generally agreed that osteolysis is a result of localized foreign-body reaction to particulate debris (e.g., cement, metal ions, UHMWPE, ceramics\* and Carbon Fibre Reinforced PEEK\*\*\*), generated by interaction between components, as well as between the components and bone, primarily through wear mechanisms of adhesion, abrasion and fatigue. It has been hypothesized that particulate debris generated by articulation of the components of a prosthesis migrate from the synovial cavity and into the boneimplant interface, where they recruit macrophages and stimulate phagocytic action. The degree of recruitment is determined by the size, distribution and amount of particulate debris as well as the rate of debris generation. The phagocytic action has been demonstrated in vitro to induce release of cytokines and cellular mediators (IL-1, IL-2, IL-6, PGE2, TNF3). These mediators have been shown to modulate osteoclastic bone resorption. Clinical and basic research is continuing in order to better understand the scientific basis for the causes of this phenomenon and explore potential ways to reduce its occurrence.

Since osteolysis is frequently asymptomatic, the patient's normal periodic radiographic examination is a good way to detect and minimize any serious future complication. However, radiographs may not completely define the extent of osteolysis. Presence of local lesions which are progressive may necessitate replacement of the prosthetic component(s).

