Since osbolysis is frequently asymptomatic, the patient's normal periodic radiographic examination is a good way to help defect and minimize any serious future complication. However, radiographs may not completely define the extent of ostolysis. Presence of local lesions which are progressive may necesstate replacement of the prosthetic component(s).

- OTHER IMPORTANT INFORMATION

  A. Particular attention should be paid when handling those prostheses hat have some type of coating, e.g., hydroxylapatite. Contact between the coated surface and cloth or other fibre releasing materials should be avoided in order to minimize contamination of the coated surface with adherent materials. All implants where the coating has been damaged or contaminated should be discarded.
- Titanium Plasma Sprayed Devices

The United States Food and Drug Administration (FDA) believes that reasonable assurance of the safety and effectiveness of components with Titanium Plasma Sprayed surfaces has not yet been established by brig term (i.e., nine years and greater) studies. In bench testing, plasma sprayed porous coadings have shown lower mechanical strength and lower resistance b abrasion than sintered cobal chromium alloy bead coatings or sintered titanium fibre mesh coatings. Clinically, loss

of the titanium plasma sprayed coating could lead to compromise of function or failure of the device, necessitating revision. The FDA has mandated post market surveillance of these devices until such time as a nine year follow up is achieved. Patients receiving these devices should be monitored to ensure hat the plasma sprayed device is not failing earlier than reasonably expected due to metal debris, coating spalling or coating delamination. These conditions could result in significant incapacitation and require revision suggery. Short term (i.e., less than four years) clinical data have not identified any significant differences in the clinical failure rate between titanium plasma sprayed porous coated hig systems and hip systems with sintered porous coatings.

Product Label. See product label for information regarding the specific product referenced in this package insert.

C.

- How Supplied
  These products have been sterilized by either gamma radiation or hydrogen peroxide. Refer to the package label for the sterilization method.
- Do NOT resterilize.
- Take care to prevent contamination of any components.

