## Restoration®ADM X3® Acetabular System ADVERSE EVENT

| GENERAL INFORMATION                                                           |                                                                                  |                                                  |  |  |
|-------------------------------------------------------------------------------|----------------------------------------------------------------------------------|--------------------------------------------------|--|--|
| SUBJECT INITIALS:                                                             | ONSET DATE:                                                                      | SUBJECT ID:                                      |  |  |
|                                                                               |                                                                                  |                                                  |  |  |
|                                                                               | (DD-MMM-YYYY)                                                                    |                                                  |  |  |
| I. DESCRIPTION                                                                |                                                                                  | 2)                                               |  |  |
| A. OPERATIVE SITE EVENTS                                                      | heck one event in Section A or Section                                           | В)                                               |  |  |
| 
 
Acetabular Component Loosening
 
                            | Femoral Neck Crack / Fracture                                                    | 

Soft Tissue Trauma

             |  |  |
| 
 
Acetabular Insert Crack / Fracture
 
                        | Femoral Stem Crack / Fracture                                                    | 
 
Superficial Wound Infection
 
  |  |  |
| Acetabular Migration (If > 3mm)                                               | ○ Heterotopic Bone Formation (Type III / IV) ○ Tendonitis                        |                                                  |  |  |
| 

Acetabular Shell Crack / Fracture

                           | O Hip Pain                                                                       | Thigh Pain                                       |  |  |

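### Radiographs are required only to year 5, yet AE rates and radiographic data are tabulated at 10 years: late AE rates for silent events, chiefly osteolysis, are likely understated, and the 10-year radiographic table rests on opt-in sites

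*Combined protocol and SAP*

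**What the plan says.** Section 2.1.2 (Radiographic Outcomes) requires AP pelvis, AP femur and "lateral views for the preoperative, 6-week, 1, 2, 3, 4 and 5-year intervals". For later films it says: "Additional radiographs will be obtained at the 7-year and 10-year time points at investigational sites that choose to bring their subjects back in". The Evaluation Schedule also marks radiographs at 7 and 10 years as optional.

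In the second phase, section 7.4 requires only that "all subjects will complete a brief Follow-up Questionnaire annually at the 6-year, 7-year, 8-year, 9-year and 10-year follow-up intervals". The form may be completed by telephone, at home or in clinic. It covers pain, satisfaction, surgery and dislocation (Appendix F) and has no item on x-rays.

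The synopsis (Statistical Methodology, Secondary) states: "The AE rates and radiographic data will be listed and tabulated at 10 years postoperative". Section 9.2.2 reports AEs as number and percent of cases or subjects with 95% confidence intervals. Section 9.4.4.2 defines the safety population as all non-censored subjects who received shell and insert, and section 9.3 rules out imputation. Sections 2.2 and 12.3 compare the resulting rates with published ones.

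The AE form in Appendix F lists osteolysis, component loosening, femoral subsidence and "Acetabular Migration (If > 3mm") as operative-site events. The labelling in Appendix C says: "Since osteolysis is frequently asymptomatic, the patient's normal periodic radiographic examination is a good way to detect and minimize any serious future complication".

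**The concern.** Several operative-site events on the AE form are found mainly on a film. From year 6, a hip at a site that does not opt in has no scheduled film, so an event without symptoms has no study route to the AE form. The hip stays in the denominator as event-free. An AE percentage at 10 years over all implanted cases then mixes five years of scheduled imaging with five years of partial imaging and reports them as one rate. Set beside published rates, it favours the device unless the published series had a similar gap in imaging.

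The radiographic table has a different problem. The plan gives no denominator for it, no minimum number of opt-in sites and no rule for hips last filmed at year 5. Section 11.6 lists only missed required radiographs as visit deviations, so absent year-7 and year-10 films need not be logged. A reader could take the table as describing the cohort when it describes the hips whose sites chose to continue.

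**Working it through.** **The plan's own figure.** Section 9.4.2 needs 274 analysable cases and allows 20% loss: 274 / 0.80 = 342.5, rounded up to 343. This reproduces the stated figure. With 350 enrolled, 350 × 0.80 = 280 hips would be expected at year 10.

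**AE rate over all implanted hips.** Let q5 and q10 be the true cumulative proportions with the event at years 5 and 10, s the share of hips imaged at year 10, and m the share of late events found without a study film. Assume full detection to year 5 and ignore loss to follow-up. Then

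observed = q5 + (q10 − q5) × [m + (1 − m) × s].

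None of q5, q10, s or m is in the documents; all values below are assumptions. With q5 = 2% and q10 = 5%:

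| s | m = 0 | m = 0.5 |
|---|---|---|
| 0 | 2.0% | 3.5% |
| 0.25 | 2.75% | 3.9% |
| 0.50 | 3.5% | 4.25% |
| 0.75 | 4.25% | 4.6% |
| 1 | 5.0% | 5.0% |

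For example, s = 0.25 and m = 0.5 gives 2 + 3 × (0.5 + 0.5 × 0.25) = 3.875%.

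Across q5/q10 of 1/3%, 2/5% and 2/10%, with s from 0 to 0.75 and m from 0 to 0.5, the observed rate runs from 20% of the true rate (2/10, at s = 0 and m = 0) to 92.5% of it (4.625/5, at s = 0.75 and m = 0.5). The shortfall vanishes only if s = 1 or m = 1.

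**Constant-hazard version, with m = 0.** For hazard h per year, true = 1 − exp(−10h) and observed = [1 − exp(−5h)] + exp(−5h) × [1 − exp(−5h)] × s. At h = 0.01 the true rate is 9.5%, and the observed rate is 4.88 + 4.64 × s, that is 6.0%, 7.2% and 8.4% for s = 0.25, 0.50 and 0.75. At h = 0.005 a true 4.9% is observed as 3.1%, 3.7% and 4.3%. These figures are an upper limit on the understatement at each s, because they give no credit for detection outside study films.

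**Radiographic table over imaged hips.** Suppose half the hips are imaged and the true overall rate is 5%.
- Opting in unrelated to outcome: expected value 5%, no bias.
- Imaged hips worse, 7% against 3%: overall 0.5 × 7 + 0.5 × 3 = 5%, but the table reads 7%.
- Imaged hips better, 3% against 7%: the overall rate is again 5%, but the table reads 3%.

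The direction is not fixed.

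**Precision of that table.** Exact 95% intervals near a 5% rate, treating hips as independent:
- all 280 hips imaged, 14 events: 2.8% to 8.2%;
- 25% imaged, 280 × 0.25 = 70 hips, 4 events (5.7%, since 5% of 70 is 3.5): 1.6% to 14.0%.

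**The case against.** The strongest reply is that two outputs should not be merged. Section 9.2.1 defines radiographic stability at each postoperative visit, and nothing is imputed. Unimaged hips may therefore simply drop out of the 10-year radiographic table rather than count as stable. This stands: a reader might infer that the radiographic results too must be understated, but the documents leave the denominator open and do not support that.

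Second, the protocol has other routes to late events. Section 8.1 makes coordinators follow up questionable questionnaire answers and file an AE form where warranted. Section 8.1 (reporting period) requires AEs to be sought by specific questioning at each contact, and section 8.4 covers events between visits. The labelling calls only osteolysis frequently asymptomatic; section 12.2 links late loosening to bone erosion and/or pain. It is tempting to put loosening and migration on the same footing as osteolysis, but the text does not go that far. These routes raise m. They do not reach an event that causes no symptoms.

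Third, a reader might infer that the labelling contradicts the film schedule, since section 12.2 says devices are used according to labelling that states: "The FDA has mandated post market surveillance of these devices until such time" as nine-year follow-up is achieved. That does not hold either. Section 12.2 concerns use of the device, the radiographic advice refers to the patient's normal periodic examination, and the surveillance statement sets no film schedule for this study.

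Finally, these are descriptive secondary results with no test or success criterion, and the primary endpoint needs no film. That limits the stakes, but a low rate set beside published rates can still mislead.

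**Conclusion.** The concern holds for AE percentages over all implanted cases: the 10-year rates of events that can be silent are likely understated, most clearly osteolysis and less certainly migration, subsidence and loosening. The size cannot be fixed from the documents. For an assumed true 5% with 2% by year 5 and 25% to 75% of hips imaged, the observed rate is 2.75% to 4.25% if no late event is found otherwise, and 3.9% to 4.6% if half are. It is likely rather than certain, because full site opt-in or complete detection outside study films would remove it.

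For the 10-year radiographic table, the defect is a self-selected subset with no stated denominator; bias may be upward, downward or absent. Dislocation, the primary endpoint, is not affected. The matter deserves a change to the analysis plan because it alters reported rates and costs little.

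**What to change.** No procedure needs to be added.

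1. Make year 5, the last visit with required films, the main time point for radiographic stability and image-dependent AEs (osteolysis, migration, subsidence, loosening).
2. At years 7 and 10, report the number imaged. Use only hips with a scheduled study film as the denominator. For image-dependent events, censor other hips at their last scheduled film. Label the results as opt-in-site data. All reported AEs remain in the full listing.
3. Compare 5-year characteristics and findings between opt-in and other sites, and make no all-cohort 10-year claim about silent radiographic events. Bring the synopsis wording on 10-year tabulation into line with this.
4. List findings from routine-care films separately. Do not pool them into the imaged-hip rate: such films may be prompted by symptoms and would enrich the denominator with diseased hips.

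The cost is analysis-plan and table wording, a narrower 10-year radiographic statement and wider intervals. Censoring at the last film assumes that opting in is unrelated to outcome; item 3 examines that assumption but cannot prove it.

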# 9.2 Safety Parameters

# 9.2.1 Safety Parameters

Safety parameters will include

- All AEs reported
- Rate of psoas impingement
- Rate of associated groin pain (derived from the 'Operative Site Other' field on the AE form)

- Radiographic stability at each postoperative visit
- Revision or removal of any study component
- Revision or removal of the Restoration® ADM Acetabular Shell and X3®
   Acetabular Insert

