### 9.2.2 Safety Analysis

All AEs will be listed, tabulated and summarized by event, number and percent of cases/subjects. AE rates and 95% confidence intervals will be presented.

For categorical variables, such as radiographic stability, the number and percent in each category will be presented.

The Kaplan-Meier survival curve of revision/removal of any study component and the Restoration® ADM Acetabular Shell and X3® Acetabular Insert will also be displayed.

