# 10.3 Early Withdrawal of Subjects

### When and How to Withdraw Subjects

In the event that the subject is discontinued by the investigative center prior to the final study evaluation, the subject will be notified by the center that he/she is no longer in the study and a Study Termination eCRF will be completed.

The following is a list of reasons for which subjects may be withdrawn and the date of termination that should be used on the Study Termination eCRF in each situation. This list is not all inclusive:

Termination Reason	Date of Termination
Death	Date of death
Investigative center termination	Date of study close-out visit
Lost to follow-up	Date Stryker termination approval given
Voluntary withdrawal	Date subject notified center of withdrawal
Revision/removal of study device	Date of revision/removal procedure
Study device not implanted	Date of surgery
Surgery not performed	Date Stryker termination approval given

At the time of study surgery it is required that the following components are implanted for each treatment group:

Restoration® ADM X3® System with any compatible Stryker Stem:

- Restoration® ADM Acetabular Shell
- Restoration® ADM X3® Acetabular Insert

- o 28 mm Stryker femoral head (except for the LFIT™ Anatomic CoCr femoral bearing head)
- Compatible Stryker femoral stem (with a minimum of 100 Accolade® II Hip Stems)

Revision or removal of the Restoration® ADM X3® Acetabular System (acetabular shell and insert) constitutes a failure and study termination for the subject.

If femoral stem or femoral head revision is required during the study, the event is considered a reoperation and does not constitute a failure or study termination.

If the subject fails to return for his/her follow-up appointments, every effort should be made to contact the subject to assess his/her health status. If, after attempting to contact the subject through three documented phone calls and a certified letter, the subject still does not respond, he/she will be considered lost to follow-up. A Study Termination eCRF will be completed only after notifying Stryker of the subject's status and being given approval to terminate.

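### The radiographic failure rule names no component and is reported only visit by visit, so cup failure is ambiguously defined and revised cups drop out of later radiographic tables

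*Combined protocol and SAP*

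**What the plan says.** Section 2.1.2 (Radiographic Outcomes) describes two zone schemes in separate statements. For the cup: "Radiographic analysis of the acetabular component will employ three zones (Zone 1 – Zone 3) in the AP view". For the stem: "femoral component will employ seven zones (Zone 1 - Zone 7) in the AP views and seven zones (Zone 8 – Zone 14) in the lateral view". A lucency counts in a zone under this definition: "Radiolucency in at least 50% of a zone and measuring at least 1 mm in width is defined as radiolucency present". The failure rule then takes the case as its unit: "migration of greater than 5 mm in any direction or at least 2 mm radiolucency in all zones will be considered radiographic failures". Neither branch says which component it applies to.

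For reporting, Section 9.2.1 lists "Radiographic stability at each postoperative visit" as a safety parameter, and Section 9.2.2 says: "For categorical variables, such as radiographic stability, the number and percent in each category will be presented". Section 9.3 rules out imputation. Under Section 10.3, revision or removal of the acetabular system "constitutes a failure and study termination for the subject", whereas revision of the stem or head is a reoperation and the subject continues.

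Three other places bear on the point:

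- The synopsis has radiographic data tabulated at 10 years, while the Evaluation Schedule and Section 2.1.2 make the 7-year and 10-year films optional by site.
- The Adverse Event form in Appendix F lists acetabular migration with a threshold above 3 mm.
- The same form keeps cup loosening and cup migration apart from stem loosening and stem subsidence.

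**The concern.** Radiographic stability, set against other primary hip systems, is a secondary objective, and it is framed around the acetabular system. Three features make the planned summary hard to interpret.

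1. The lucency branch can be read in two ways, and the two readings classify a fully lucent cup differently.
2. The migration branch lets a subsiding stem make the case a failure, although stems differ across cases: at least 100 are Accolade II and the rest are any compatible stem from the sponsor.
3. A percentage at each visit describes the cups still in the study and filmed at that visit. If failed cups tend to be revised, and revision ends participation, the later percentages omit the cases of most interest. No cumulative count is planned to restore them.

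**Working it through.** The plan gives no expected radiographic failure rate, sample size or precision target, so there is no stated figure to reproduce. The check is a comparison of readings followed by illustrative arithmetic.

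**Step 1: the rule under two readings.** Zones from Section 2.1.2: 3 cup + 7 stem (AP) + 7 stem (lateral) = 17. The labels 1 to 3 occur in both schemes, so zone numbers do not settle which zones are meant.

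| Film finding | All zones = cup and stem together | All zones = one component |
|---|---|---|
| Cup lucent by 2 mm or more in 3 of 3 cup zones, stem clear, no migration above 5 mm | Not a failure (3 of 17 zones) | Failure |
| Same lucency, cup also migrated more than 5 mm | Failure | Failure |
| Cup sound, stem subsided more than 5 mm | Failure | Failure |

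The first row turns on interpretation. The third row gives a case-level failure on either reading, because the migration branch names no component. Even on the component reading, the text does not say whether the stem needs its 7 AP zones or all 14.

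**Step 2: what happens after revision.** Section 10.3 ends participation at cup-system revision, Section 9.3 imputes nothing, and Sections 9.2.1 and 9.2.2 give number and percent per visit. No carry-forward rule or visit denominator is written. It follows, by inference, that a cup failed at year 2 and revised before year 3 adds nothing to the radiographic tables at years 3, 4 and 5.

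**Step 3: possible size.** N = 350 is the enrollment in Section 9.4.2. The rest is assumed: all cups are filmed; F failures are spread evenly over the five annual visits; a share s of those first seen at years 1 to 4 is revised before the 5-year film; unrevised failures continue to be read as failures.

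- Earlier failures E = 4F/5; failures first seen at year 5 = F/5.
- 5-year table = [F/5 + E(1 − s)] / (N − E·s).
- Cumulative = F/N.

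| F | Cumulative | s = 0 | s = 0.5 | s = 1 |
|---|---|---|---|---|
| 5 | 5/350 = 1.43% | 5/350 = 1.43% | 3/348 = 0.86% | 1/346 = 0.29% |
| 10 | 10/350 = 2.86% | 10/350 = 2.86% | 6/346 = 1.73% | 2/342 = 0.58% |
| 20 | 20/350 = 5.71% | 20/350 = 5.71% | 12/342 = 3.51% | 4/334 = 1.20% |

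On these assumptions the 5-year percentage never exceeds the cumulative one, and the gap runs from nothing (s = 0) to a ratio of (10/350)/(2/342) = 4.9 for F = 10 and s = 1.

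**The case against.** The strongest reply is that the text does not require a pooled 17-zone reading. Cup and stem are introduced as separate analyses with overlapping labels, so reading the rule per component is at least as natural. That stands: the defect is ambiguity. A reader might infer that the rule lets loose cups escape, but the documents do not support this as a general statement. Escape needs the pooled reading and no migration above 5 mm. Cup loosening is also reportable as an operative-site adverse event whatever its seriousness (Section 8.1 and the Adverse Event form).

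A reader might also infer that a revised cup vanishes from the results. It does not. If filmed and classed as failed, it is in the earlier visit's table. It is in the adverse event tables, unless censored for a protocol deviation under Section 9.4.4.4. Its revision enters the Kaplan-Meier curves of Section 9.2.2. The loss is confined to radiographic tables after revision. The curves and event tables do not fill that gap, however, because they estimate revision and event rates, not radiographic failure.

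Combining cup and stem can be defended, since Section 1.1 says that the study also collects longitudinal data on the Accolade II stem. That is a reason to report stem failure, but separately from the cup.

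**Conclusion.** The point holds as a matter of incomplete definition and a missing summary. The classification of a fully lucent cup depends on how the rule is read, stem migration is mixed into a summary meant for the acetabular system, and no cumulative radiographic count is planned.

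The size cannot be fixed from the documents. With 10 assumed failures, the 5-year figure lies anywhere from 0.58% to 2.86% against a cumulative 2.86%, depending on how many earlier failures are revised. Two stronger conclusions are not supported. One is a fixed several-fold understatement, because the range includes none at all. The other is that the by-visit percentage must improve over time, because unrevised failures remain and new ones accrue. Nor do the documents say whether the published comparators are cumulative; a cumulative figure is needed if they are.

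The endpoint is secondary and descriptive with no test attached, so this is a worthwhile correction that does not affect the primary conclusion.

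**What to change.** - State the rule by component, leaving the Section 2.1.2 thresholds as they stand. Cup failure: cup migration above 5 mm, or lucency of at least 2 mm in all of cup zones 1 to 3. Stem failure: stem migration above 5 mm, or lucency of at least 2 mm in all of stem zones 1 to 14.
- Report cup and stem failure separately, with the Accolade II cases shown on their own.
- Beside the by-visit table, add a cumulative ever-failed table by visit. Keep earlier failures in numerator and denominator, count revision for loosening or migration as failure, and give the denominator at each visit.
- Reconcile the migration threshold in Section 2.1.2 (above 5 mm) with that on the Adverse Event form (above 3 mm), or explain why they differ. This review takes no position on which should apply.
- Reconcile the synopsis's tabulation at 10 years with films that are optional by site at that visit.

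The cost is protocol wording and one added table. The independent reviewer already reads the zones, so no new films or readers are needed. The reported failure rate may be slightly higher.
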